4.3.1. Definition of Endpoint

The primary efficacy comparison will be based on the contrast between each treatment group of LY3561774 and placebo for the mean percent change of ApoB between randomization at Visit 2 and Day 180.

4.3.2. Main Analytical Approach

Mean percent change of ApoB will be analyzed using the MMRM model for the efficacy estimand. As described in Section 4.1, the response variable will be log-transformed.

A restricted maximum likelihood-based MMRM analysis will be used to analyze continuous longitudinal variables. All longitudinal observations taken at each scheduled postbaseline visit will be included in the analysis. The model for the analysis of the primary efficacy endpoint of percent change from baseline in ApoB will include the fixed class effects of treatment group (placebo, LY3561774 100 mg, LY3561774 400 mg, and LY3561774 800 mg), visit, treatment-by-visit interaction, Visit 1 TG stratum (lower than 250 mg/dL, 250 mg/dL or greater) as well as the continuous baseline value of the log-transformed dependent variable.

An unstructured covariance structure will be used to model the within-participant errors. Significance tests will be based on LS means and type III tests. If this analysis fails to converge, these covariance structures will be tested in order

- Toeplitz with heterogeneity
- autoregressive with heterogeneity
- compound symmetry with heterogeneous variances
- Toeplitz
- · autoregressive, and
- compound symmetry without heterogeneous variances.

The first covariance structure that converges will be used. The Kenward-Roger approximation will be used to estimate denominator degrees of freedom.

4.4. Secondary Endpoints Analysis

4.4.1. Analyses Using the Efficacy Analysis Set

The secondary study objectives will be analyzed with the efficacy estimand using the data in the EAS. The clinical measures for secondary endpoints may be log-transformed before statistical analyses, if deemed necessary.

Percent change from baseline at Day 180 for

- angiopoietin-like protein 3 (ANGPTL3)
- LDL-C
- HDL-C
- non-HDL-C, and
- TG

Percent change from baseline at Day 270 for

- ANGPTL3
- ApoB
- LDL-C
- HDL-C

- non-HDL-C, and
- TG.

Mean percent change of the above endpoints will be analyzed using the MMRM model for the efficacy estimand as described in Section 4.3.2.

4.5. Exploratory Endpoints Analysis

Unless otherwise specified, exploratory analyses will be conducted for the EAS using the general methods detailed in Section 4.1.

4.5.1. Analyses using the Efficacy Analysis Set

These two exploratory study objectives will be analyzed using the EAS and the associated efficacy estimand.

Percent change from baseline at Day 180 for

- high-sensitivity C-reactive protein (hsCRP)
- apolipoprotein A-I (ApoA-I)
- apolipoprotein C-III (ApoC-III)
- VLDL-C
- urine albumin/creatinine ratio (UACR)
- hemoglobin A1c (HbA1c), and
- fasting glucose (FG).

Percent change from baseline in time-averaged parameters over Days 30 to 180 and Days 120 to 270 for

- non-HDL-C
- LDL-C
- HDL-C
- ApoB, and
- TG.

These endpoints will be analyzed using the MMRM modeling strategy as detailed in Section 4.3.2. Comparisons of difference in time-averaged response from baseline for treatment group k versus placebo reference group, indexed by R, will be made by using contrasts of LS means to calculate

$$\hat{\theta}_{\Delta k} = \hat{\mu}_{1k} - \hat{\mu}_{1R} + \sum_{t} w_t \left(\hat{\beta}_{k:t} - \hat{\beta}_{R:t} \right),$$

where $\hat{\mu}_{1k}$ is the coefficient corresponding to treatment group k, $\hat{\beta}_{k:t}$ corresponds to the treatment-time interaction coefficient, R represents the placebo reference group, and w_t is the weight at time t informed by the trapezoidal rule. Estimates and CIs will be constructed from the model-based versions using the delta method. An overall test of significance will be conducted using the F-test under the null hypothesis that $\theta_{\Delta k}=0$ for all LY3561774 arms simultaneously.

4.5.2. Analyses using the Full Analysis Set

These two exploratory study objectives will be analyzed using the full analysis set (FAS) and the associated treatment-regimen estimand.

Absolute change from baseline at Day 180 for

- non-HDL-C
- LDL-C
- HDL-C
- ApoB, and
- TG.

Percent change from baseline at Day 180 for

- non-HDL-C
- LDL-C
- HDL-C
- · ApoB, and
- TG.

Missing data for the dependent variables at each time point will be imputed using multiple imputation as detailed in Section 4.1.

4.5.3. Pharmacokinetic and Pharmacokinetic/Pharmacodynamic Methods

Pharmacokinetic (PK), pharmacodynamic (PD), and PK/PD analysis are the responsibility of Lilly's PK/PD group.

A population PK approach using nonlinear mixed-effects modeling will be used to analyze LY3561774 concentration data.

Exposure-response analysis between LY3561774 concentration and safety, pharmacology, and efficacy may be performed using population PK and population PK/PD nonlinear mixed-effects modeling techniques implemented on Nonlinear Mixed Effects Modeling (NONMEM®) software.

Additionally, the impact of intrinsic and extrinsic factors, such as age, weight, gender, and liver function on PK and PD parameters may be examined as needed.

If anti-drug antibody (ADA) titers are detected from immunogenicity testing, then the impact of immunogenicity titers on LY3561774 PK, or any other relevant efficacy parameters, may also be examined. Additional analyses may be conducted if deemed appropriate.

4.5.4. Bayesian Analyses for Dose-Response

A Bayesian dose-response analysis will be performed on the percent change from baseline at Day 180 and the percent change from baseline for time-averaged parameters from Day 30 to Day180 and from Day 120 to Day 270 for the parameters

- ApoB, and
- non-HDL-C.

The longitudinal model, a proportional discrete time model (PDT), will be used to estimate Bayesian dose response. The PDT model assumes that the efficacy of the modelled treatment plateaus after some time point, Q. Let $y_{it}(d)$ represent the change from baseline ApoB at time t for participant i receiving dose d. Then the PDT can be written as

$$y_{it}(d) = \mu(t_l, d, \theta) + g(t) * s_i + \epsilon_{it}$$

with the mean function

$$\mu(t_l, d, \theta) = \lambda(d) \{ p_l * I(t_l < t_0) + I(t_l \ge t_0) \}$$

where $s_i \sim N(0, \sigma_s^2)$ and $\epsilon_{it} \sim N(0, \sigma^2)$, $\theta = (\lambda(d), p_1, ..., p_{Q-1})'$, and p_l represents the proportion of the efficacy of dose level d, $\lambda(d)$, at time t_l , for $t_l < t_Q$. Based on the data from the above, we may assume $t_Q = \text{Day } 30$. The function, g(t), may be specified to allow the errors to be proportional to the time trend of the mean response. An example of such a function that also incorporates a plateau in efficacy (Qu et al. 2019) is

$$g(t) = \{p_l * I(t_l < t_Q) + I(t_l \ge t_Q)\}.$$

A simple normal dynamic linear model may be assumed for the dose-response function, $\lambda(d)$:

$$\lambda(1) \sim N(0, \sigma_{\lambda}^{2})$$
$$\lambda(d) \sim N(\lambda(d-1), \sigma_{\lambda}^{2}) \text{ for } d > 1$$

The estimation of the parameters will be carried out in a Bayesian framework, assuming non-informative priors for the hyperparameters:

$$p_l \sim U(0,1)$$

$$1/\sigma^2, 1/\sigma_s^2, 1/\sigma_\lambda^2 \sim Gamma(0.01, 0.01)$$

Posterior inference will be drawn for the dose response at time t of clinical interest and the 95% credible intervals will also be plotted.

Alternative dose-response models, including the three-parameter logistic regression or power model, may also be considered for $\lambda(d)$, if the dose-response model does not fit the data well. Some alternative dose-response models are

• Three-parameter logistic model

$$\lambda(d) = \alpha_0 + \frac{\alpha_1 d^*}{\alpha_2 + d^*}$$

where parameters α_0 , α_1 , and α_2 represent the basal effect when the dose level is zero (placebo), the maximum effect that can be achieved by any dose level on top of placebo, and the dose level that produces half of the maximum improvement (ED₅₀), respectively. Here, d*, represents the actual dose (for example, in mg) versus dose level (1, 2, 3, and so on).

Power model

$$\lambda(\mathbf{d}) = \alpha_0 * \alpha_1 \mathbf{d}^{*\gamma}$$

where α_0 and α_1 represent the basal effect for the placebo group and the slope, respectively, and γ is a sigmoidicity parameter indicating shape or steepness of the dose response. Here, d^* , represents the actual dose (for example, in mg) versus dose level (1, 2, 3, and so on).

Furthermore, if the PDT model, or any related longitudinal model, does not fit the data well, these or other dose-response models may be fitted to the percent change from change from baseline at Day 180, and the percent change from baseline for time-averaged parameters from Day 30 to Day 180 and from Day 120 to Day 270 for the parameters, excluding the intermediate timepoints.

The same dose-response models may be fitted to the percent absolute change from baseline for magnetic resonance imaging (MRI) hepatic fat fraction at Day 180 and the time-averaged endpoints. These models will not require additional longitudinal modeling, and will take place after imputation for missing data according to the efficacy estimand for the time-averaged analysis and the treatment policy estimand for the hepatic fat fraction analysis.

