9.3.4. Tertiary/Exploratory Analysis

Exploratory endpoints are listed in Section 3.

The average of AUC (Day 120-180) and AUC (Day 210-270) of the ApoB reduction will be calculated for participants with complete ApoB measurements during the specified period.

The calculated AUCs will be analyzed using an ANCOVA model. Baseline ApoB measurements will be used for adjustment. A Bayesian approach will be used as the dose-response model for time averaged AUC measures. The placebo group will be modeled with LY3561774 doses.

Details of the prior distribution specifications along with other analyses used for the exploratory objectives will be provided in the SAP.

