9.5. Sample Size Determination

The sample size calculation is based on the primary efficacy estimand and its endpoint, percent change from baseline at Day 180 in ApoB.

Approximately 175 participants will be randomly assigned in a 2:1:2:2 ratio to placebo: LY3561774 100 mg:400 mg:800 mg. Assuming a 20% dropout rate, this results in approximately 20 completers for 100 mg group and 40 completers per arm for the rest of the groups.

Assuming a standard deviation of 15%, and a 2-sided alpha level of 0.05, the completers for each treatment arms will provide >99% power to detect a treatment difference of -30% for the primary endpoint.

10. Supporting Documentation and Operational Considerations

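### The Bayesian dose-response model in SAP 4.5.4 has no term for baseline or Visit 1 TG stratum; adding both is a cheap gain in precision for an exploratory analysis

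*SAP*

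**What the plan says.** SAP 4.5.4 plans a Bayesian dose-response analysis of ApoB and non-HDL-C at Day 180 and over two time-averaged windows: "The longitudinal model, a proportional discrete time model (PDT), will be used to estimate Bayesian dose response". The response y is said to "represent the change from baseline ApoB at time t for participant i receiving dose d". Its mean is lambda(d) times a proportion p_l before the plateau time, and lambda(d) alone from then on; the section suggests Day 30 for that time. A participant effect and a residual error are added. The parameter vector of the mean holds only lambda(d) and the p_l. The alternatives for lambda(d), a three-parameter logistic and a power model, depend on dose alone.

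Elsewhere the plan adjusts. The MMRM in SAP 4.3.2 includes the Visit 1 TG stratum "as well as the continuous baseline value of the log-transformed dependent variable". SAP 4.5.1 cites Section 4.3.2 for the time-averaged endpoints. Protocol 9.3.4 says of the ANCOVA of AUCs: "Baseline ApoB measurements will be used for adjustment". SAP 4.5.4 does not cite 4.3.2. The general rule in SAP 4.5 points to Section 4.1, which does not list the covariates.

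**The concern.** ApoB is not a stratification factor, so arms can differ in baseline ApoB by chance, most easily in the small 100 mg arm. Change from baseline is usually correlated with baseline. A model without that covariate leaves the predictable part of the response in the noise. The participant effect s_i does not solve this: it has mean zero and unexplained variance, and that variance enters every between-arm contrast. A baseline term would explain part of it.

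Precision matters more here than in the primary analysis. An effect of 30 points against placebo is easy to detect, but a dose-response model has to resolve smaller gaps between doses. SAP 4.1 says that the trial is not adequately powered for differences among doses and does not plan such comparisons unless otherwise specified. Exposure-response modelling (SAP 4.5.3) is optional.

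**Working it through.** **Inputs from the documents (Protocol 9.5).** The size and allocation are: "Approximately 175 participants will be randomly assigned in a 2:1:2:2 ratio to placebo: LY3561774 100 mg:400 mg:800 mg". Dropout is put at 20%, which leaves about 20 participants at 100 mg and 40 in each other group. The spread and test level are: "Assuming a standard deviation of 15%, and a 2-sided alpha level of 0.05". The claim for each dose is ">99% power to detect a treatment difference of -30% for the primary endpoint".

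**The plan's own figure.** 175 × (2, 1, 2, 2)/7 = 50/25/50/50 randomized; × 0.8 = 40/20/40/40 completers. SE = 15 × sqrt(1/n1 + 1/n2):

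- 40 v 40: 15 × sqrt(0.05) = 3.35 points; 30/3.35 = 8.9 SEs.
- 20 v 40: 15 × sqrt(0.075) = 4.11 points; 30/4.11 = 7.3 SEs.

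Normal and noncentral t calculations both give power above 99.99%, so the stated figure reproduces.

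**Assumptions not in the documents.** Baseline and each follow-up visit have the same variance. All pairs of visits within an arm have the same correlation r, taken as 0.6 to 0.9.

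**One visit.** The correlation of change with baseline is −sqrt((1 − r)/2), so adjustment removes (1 − r)/2 of the variance. Adjusted/unadjusted SE = sqrt((1 + r)/2).

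**Plateau mean.** If the effect is flat from Day 30, lambda(d) is in effect estimated from an average of visits. Days 30, 60, 90, 120, 150 and 180 give m = 6. For the mean of m visits, adjusted/unadjusted SE = sqrt((mr + 1)/(m + 1)).

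| r | One visit: SE ratio (cut) | Six visits: SE ratio (cut) |
|---|---|---|
| 0.6 | 0.894 (10.6%) | 0.811 (18.9%) |
| 0.7 | 0.922 (7.8%) | 0.862 (13.8%) |
| 0.8 | 0.949 (5.1%) | 0.910 (9.0%) |
| 0.9 | 0.975 (2.5%) | 0.956 (4.4%) |

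At one visit, the SE for 100 mg v placebo falls from 4.11 to 3.67 (r = 0.6) or 4.00 (r = 0.9). For 40 v 40 it falls from 3.35 to 3.00 or 3.27.

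For the six-visit mean, the unadjusted SD of change is 15 × sqrt((m + 1)/(2m)) = 15 × sqrt(7/12) = 11.46. The 40 v 40 SE is 11.46 × sqrt(0.05) = 2.56. It falls to 2.56 × 0.811 = 2.08 or 2.56 × 0.956 = 2.45.

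**Noise and imbalance are one loss.** Take 100 mg v placebo, one visit, r = 0.6. The unadjusted variance is 225 × 0.075 = 16.875. The part due to chance baseline differences is 20% of that, 3.375. Its square root, 1.84 points, is the shift from a one-standard-error baseline imbalance. The remaining 13.5 is the adjusted variance (3.67²). The imbalance is thus already inside the unadjusted SE.

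**Check under the SAP's prior.** A simulation fitted the normal dynamic linear prior with the stated gamma hyperpriors to six-visit participant means. It used 40/20/40/40 completers, assumed true effects of 0, −15, −25 and −30, and 200 replicates per setting. The adjusted/unadjusted SD of dose contrasts was 0.85 to 0.93 at r = 0.7 and 0.93 to 0.95 at r = 0.8. Mean estimates with and without the baseline term agreed within about 0.1 point. The unadjusted SD of the 800 v 400 mg contrast was 2.3 to 2.5, against a true gap of 5.

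**Unequal variances.** With k = follow-up SD/baseline SD, the share of one-visit variance removed is (kr − 1)²/(1 + k² − 2kr). At r = 0.7:

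- k = 1: 0.09/0.60 = 15%.
- k = 1.3: 0.0081/0.87 = about 1%, and zero at k = 1/r.
- k = 0.8: 0.1936/0.52 = 37%.

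The table is therefore not a bound in either direction.

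**The case against.** The strongest reply is that little depends on this. Sections 4.3.2, 4.4.1 and 4.5.1 already give baseline- and stratum-adjusted estimates of each dose against placebo, for ApoB and non-HDL-C, at Day 180 and over both windows. Those are the endpoints that 4.5.4 models. The analysis is exploratory, the gain rests on quantities that the documents do not supply, and the section is worded permissively. All of that stands, and it limits the weight of the point. It does not supply the missing terms: an analyst following 4.5.4 would fit none.

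Several stronger readings are tempting, and the documents do not support them:

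- *That this is the only analysis across doses.* It is the only dose-response analysis that the SAP commits to, but exposure-response modelling is also a listed objective, and the adjusted MMRM estimates can be set side by side.
- *That dose selection rests on this model.* The protocol says that the study's data will inform dose decisions; it does not name this model as the tool.
- *That chance imbalance biases the estimates on top of the added noise.* It is part of the variance, as shown above.
- *That the TG stratum may be badly unbalanced.* Randomization is stratified on it, so leaving it out costs precision at most. No figure for that cost can be derived from the documents.
- *That a protocol commitment is broken.* The sentence in Protocol 9.3.4 concerns the ANCOVA of AUCs. The SAP keeps baseline adjustment for the time-averaged endpoints through the MMRM.
- *That y is in mg/dL.* Section 4.5.4 opens with percent change as the target, and Section 4.1 log-transforms such endpoints. The definition of y is loose wording that should be tightened.

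**Conclusion.** The dose-response model in SAP 4.5.4 departs without explanation from the adjustment used in 4.3.2 and 4.5.1. The cost is precision only. With equal variances and r of 0.6 to 0.9, adjustment would cut standard errors by about 11% to 2.5% at one visit, or about 19% to 4% for a six-visit plateau mean. In participants, one visit is worth 1/0.80 to 1/0.95, about 25% to 5% more; the six-visit mean is worth 7/4.6 to 7/6.4, about 52% to 9% more. These sizes are conditional: the gain can vanish if follow-up variance is larger, and can exceed the range if it is smaller. Neither the primary result nor the stated power is affected. This is a worthwhile, nearly free improvement to an exploratory analysis.

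**What to change.** In SAP 4.5.4:

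1. Add two linear terms to the PDT mean and to each fallback model: centred log baseline of the modelled parameter (ApoB or non-HDL-C) and the Visit 1 TG stratum.
2. Make both terms additive and not scaled by p_l, so that the baseline relation does not grow with the drug effect. Give the coefficients weakly informative priors and state them.
3. Report lambda(d) at the mean baseline, averaged over the strata.
4. Define y as the log ratio to baseline, in line with Sections 4.1 and 4.3.2.

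If the terms are left out on purpose, say why. The cost is two more parameters, their priors and a few sentences; both covariates are already collected and used in the MMRM. Results from this model and the MMRM will still differ somewhat, because this one imposes a plateau and shrinks across doses.

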For continuous measures, summary statistics will include sample size, mean, standard deviation (SD), median, minimum, and maximum for both the actual and the change from baseline measurements. Least squares (LS) means and standard errors derived from the analysis models, mixed model repeated measures (MMRM) and analysis of covariance (ANCOVA) will also be displayed for the change from baseline measurements. Treatment comparisons will be displayed showing LS means and 95% CIs for treatment differences, along with p-values for treatment comparisons. For categorical measures, summary statistics will include sample size, frequency, and percentages. A logistic regression model will be used to examine the treatment difference in binary efficacy outcomes with missing endpoints imputed. Fisher's exact test or Pearson's chi-square test will be used for treatment comparisons in other categorical outcomes.

For analyses of efficacy parameters involving an ANCOVA model, missing data will be imputed using the multiple imputation method under the missing at random assumption. Such an approach is valid when the propensity for a data point to be missing is not related to the missing data, but is related to some of the observed data. Estimates and standard errors from multiple imputed datasets will be combined using Rubin's rules.

Endpoints that compare treatment groups based on percent change from baseline will be conducted by log-transformation of the dependent variables. Standard errors and 95% CIs will be constructed using the delta method. The LS means and standard error for each treatment, difference in LS means between arms, and corresponding 95% CIs will be calculated as shown in Table EZCB.4.1, where Z_b is the baseline of the log of the response.

Table EZCB.4.1 Summary of Reported Quantities for Variables Requiring Log-Transformation

Qua	nntity	Change from Baseline	Percent Change from Baseline
Within	Estimate	$\left[\exp\left(\hat{\mu}_{\Delta Z,k} ight) - 1 ight]\exp(ar{Z}_{b\cdot})$	$\left[\exp\left(\hat{\mu}_{\Delta Z,k}\right)-1\right] imes 100$
Treatment	SE	$\exp(\overline{Z}_{b.})\exp(\hat{\mu}_{\Delta Z,k})\cdot\widehat{SE}_{\Delta Z,k}$	$\exp(\hat{\mu}_{\Delta Z,k}) \cdot \widehat{SE}_{\Delta Z,k} \times 100$
	P-value	NR	p_k
Between- Treatment Difference	Estimate	$[\exp(\hat{\mu}_{\Delta Z,k}) - \exp(\hat{\mu}_{\Delta Z,R})] \cdot \exp(\bar{Z}_b)$	$(\exp(\hat{\mu}_{\Delta Z,k\ vs\ R})-1)\times 100$

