4.9. Changes to Protocol-Planned Analyses

The description of the EAS was amended to exclude participants who experienced permanent discontinuation of intervention, initiation of excluded medications taken during the study, and new initiation of any lipid-lowering drug required to be on a stable regimen prior to treatment per the Study EZCB protocol inclusion criteria. In the Study EZCB protocol, the EAS was described as only excluding measurements based on permanent discontinuation of intervention. This change is intended to align the analyses based on the EAS with the description of the primary estimand, based on the hypothetical strategy.

For the exploratory analysis of time-averaged endpoints, the days of time-averaging have been augmented from Day 120 to Day 180 to Day 30 to Day 180, and from Day 210 to Day 270 to Day 120 to Day 270. The purpose of this change is to capture a broader measure of effectiveness over time to accompany our other analyses at specific time points.

5. Sample Size Determination

The sample size calculation is based on the primary efficacy estimand and its endpoint, percent change, from baseline at Day 180 in ApoB.

Approximately 175 participants will be randomly assigned in a 2:1:2:2 ratio to placebo: LY3561774 100 mg:400 mg:800 mg. Assuming a dropout rate, this results in approximately 20 completers for the 100 mg group and 40 completers per arm for the rest of the groups.

Assuming a standard deviation of 15%, and a 2-sided alpha level of 0.05, the completers for each treatment arm will provide greater than 99% power to detect a treatment difference of -30% for the primary endpoint.

6. Supporting Documentation

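### With the suggested Day 30 plateau, the Bayesian dose-response model returns one number for Day 180 and both time windows, and it cannot show fading or dose differences in durability

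*SAP*

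**What the plan says.** SAP Section 4.5.4 applies a Bayesian dose-response analysis to ApoB and non-HDL-C. The targets are the percent change at Day 180 and the "percent change from baseline for time-averaged parameters from Day 30 to Day180 and from Day 120 to Day 270". The section names the PDT as the longitudinal model to be used and states its key assumption: "The PDT model assumes that the efficacy of the modelled treatment plateaus after some time point, Q".

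The mean is λ(d) times `p_l` before the plateau time `t_Q`, and λ(d) from `t_Q` on. Each `p_l` has a uniform prior on (0, 1) and no dose index. On the plateau time the section says "Based on the data from the above, we may assume" Day 30. It offers no other value, and the section as published shows no data in support.

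Two later statements in Section 4.5.4 bear on this:

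- If the PDT or a related longitudinal model "does not fit the data well, these or other dose-response models may be fitted to the percent change" at Day 180 and to the time-averaged percent changes, leaving out the intermediate visits. No criterion for poor fit is given.
- The same dose-response models may be fitted to hepatic fat fraction and to the time-averaged endpoints. Of these it says "These models will not require additional longitudinal modeling", and that the fitting "will take place after imputation for missing data according to the efficacy estimand for the time-averaged analysis".

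SAP Section 4.9 explains why the windows were widened from those in the protocol: "The purpose of this change is to capture a broader measure of effectiveness over time to accompany our other analyses at specific time points". Protocol Section 9.3.4 plans the Bayesian dose-response on time-averaged AUC and names no plateau model.

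**The concern.** The two windows are there to describe effect over time. Under the default model with the suggested plateau they cannot do so, because they equal the Day 180 value by construction.

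The last dose is given at about Day 90, so Day 270 is about 180 days after it. Protocol Section 4.2 makes measuring the return of ApoB to baseline a purpose of follow-up, and expects the 270-day period to inform dose level and frequency. Whether the effect lasts, and whether that depends on dose, is what a dose-response summary over Days 120 to 270 could show. This model can show neither. If the effect does fade, its single pooled value is biased for the targets, by amounts that depend on when fading starts.

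The text also leaves open which method applies. One part of Section 4.5.4 assigns the time-averaged targets to a longitudinal model, and another says they need none.

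**Working it through.** **Inputs.** The mean function, priors and targets are from SAP Section 4.5.4. The definition of a time average as trapezoidal AUC divided by length is from SAP Section 4.1. Visits are from the protocol schedule. SD 15, effect -30% and completers are from Protocol Section 9.5. The completer counts reproduce: 175 × (2, 1, 2, 2)/7 = 50, 25, 50, 50, and × 0.8 = 40, 20, 40, 40. So does the stated power above 99%: for 20 against 40, the SE is 15 × √(1/20 + 1/40) = 4.11, and 30/4.11 = 7.3. The power figure is not in dispute.

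**Step 1: algebra, no assumptions.** With visits every 30 days, the trapezoid weights for Days 30 to 180 (and likewise Days 120 to 270) are 0.1, 0.2, 0.2, 0.2, 0.2, 0.1, which sum to 1. With `t_Q` = Day 30 the mean is λ(d) at every one of these visits. So Day 180 = Days 30 to 180 = Days 120 to 270 = λ(d).

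**Step 2: other plateau times.** A later `t_Q` can separate the targets. For example, with `t_Q` = Day 60, Day 30 carries its own `p_l`. But `p_l` is below 1, so no visit before `t_Q` can have a larger effect than the plateau: the effect cannot end below an earlier level. Because `p_l` has no dose index, the ratio of two doses' effects is the same at every visit.

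**Step 3: size if the effect fades.** Assumed, because the documents give no time course: placebo 0, plateau -30%, linear fading, `t_Q` = Day 30, all nine visits from Day 30 to Day 270 fitted, no missing data. With the SAP's example g(t), the errors are exchangeable from Day 30, so the plateau estimate is essentially the plain visit mean. For fading from Day 180 to -10% at Day 270:

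- PDT: (6 × -30 - 23.33 - 16.67 - 10)/9 = -25.6
- True Days 120 to 270: 0.1 × -30 + 0.2 × (-30 - 30 - 23.33 - 16.67) + 0.1 × -10 = -24.0

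| Fading from, to Day 270 value | PDT, all targets | True Day 180 | True Days 30-180 | True Days 120-270 |
|---|---|---|---|---|
| none | -30.0 | -30.0 | -30.0 | -30.0 |
| Day 180, to -20 | -27.8 | -30.0 | -30.0 | -27.0 |
| Day 180, to -10 | -25.6 | -30.0 | -30.0 | -24.0 |
| Day 150, to -20 | -27.2 | -27.5 | -29.75 | -26.0 |
| Day 150, to -10 | -24.4 | -25.0 | -29.5 | -22.0 |
| Day 120, to -20 | -26.7 | -26.0 | -29.2 | -25.0 |
| Day 120, to -10 | -23.3 | -22.0 | -28.4 | -20.0 |

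A Gibbs fit with the SAP priors agrees. For fading from Day 180 to -10%, the PDT gives -25.3 for 800 mg; direct fits give -29.6, -29.8 and -23.7. In a simulation of 100 trials per scenario (correlation 0.7, fading from Day 180 to -15), coverage of the 95% credible interval for 800 mg was 50%, 50% and 95% for the three targets. With no fading it was 93 to 97% across arms.

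**Step 4: gap between doses.** Let 800 mg hold at -30 while 400 mg fades to -10 at Day 270. The PDT reports one gap.

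| 400 mg fades from | PDT gap | True Day 180 | True Days 30-180 | True Days 120-270 |
|---|---|---|---|---|
| Day 180 | 4.4 | 0 | 0 | 6.0 |
| Day 150 | 5.6 | 5.0 | 0.5 | 8.0 |
| Day 120 | 6.7 | 8.0 | 1.6 | 10.0 |

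**Step 5: precision cost of the direct fit.** For 40 against 40 the single-visit SE is 15 × √(2/40) = 3.35. At within-participant correlation ρ (assumed), multiply by √((1 + 8ρ)/9) for the nine-visit PDT and by √(ρ + 0.18(1 - ρ)) for a window, where 0.18 is the sum of squared weights.

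| ρ | PDT factor | Window factor | Ratio |
|---|---|---|---|
| 0.4 | 0.683 | 0.713 | 1.04 |
| 0.6 | 0.803 | 0.820 | 1.02 |
| 0.8 | 0.907 | 0.914 | 1.01 |

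At ρ = 0.6 the SEs are 2.69 (PDT), 2.75 (direct window) and 3.35 (direct Day 180).

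**The case against.** **Day 180 is a trade-off.** A reader might infer that the direct fit should lead for all three targets. The figures do not support that for Day 180. Combining bias and SE at ρ = 0.6 as √(bias² + SE²), the nine-visit PDT beats the direct fit's 3.35 in five of the seven cases in Step 3. It loses only for fading from Day 180: √(2.22² + 2.69²) = 3.5 and √(4.44² + 2.69²) = 5.2. This stands. It depends on the visits used, however. On the six visits from Day 30 to Day 180 the PDT has SE 3.35 × √((1 + 5 × 0.6)/6) = 2.74 and no Day 180 bias if fading starts at Day 180. With fading from Day 120 to -10 it gives (4 × -30 - 26 - 22)/6 = -28 against a true -22. Neither method wins throughout.

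**The fallback would probably be used.** With 40 in an arm and ρ = 0.6, Day 270 minus the mean of the six visits from Day 30 to Day 180 has SE √(225 × 0.4 × (1 + 1/6)/40) = 1.6. A 10-point fade is about 6 SE and would be hard to miss, and the by-visit MMRM would show it too. This largely stands for big fades. But the fallback is optional and has no criterion, and with Day 30 the windows repeat Day 180 whether or not anything fades.

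**The last paragraph may already assign the windows to a direct fit.** On that reading the problem does not arise for them. But the same section names the PDT for those targets and offers direct fits to them as a fallback. The statements conflict, and the later one does not clearly override the earlier.

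**The illustration needs data to Day 270.** The SAP does not say which visits enter the PDT, and the primary lock comes when all participants have completed Day 180. The pooled values apply only if all nine visits are fitted. The algebra in Steps 1 and 2 does not need this.

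**Decision relevance.** The protocol's remark about dose level and frequency concerns the length of the study, not this model. That is fair, and limits the weight of the point.

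**Conclusion.** The structural point holds by algebra. With Day 30 as plateau, the three targets are one parameter and the windows cannot serve the purpose given in SAP Section 4.9. At any plateau time among the fitted visits, an effect that ends below an earlier level, or durability that differs by dose, cannot appear.

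The size is conditional. With no fading there is no bias. In the assumed fading cases, Days 30 to 180 is understated by 2.2 to 5.1 points and Days 120 to 270 overstated by 0.8 to 3.3. Day 180 ranges from 4.4 understated to 1.3 overstated. These rest on linear fading, a -30% plateau and all nine visits.

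Three stronger readings are not supported:

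- That the effect is known to fade. Protocol Section 2.2 reports Phase 1 effects on ANGPTL3, triglycerides and LDL-C continuing to the last collection point at Day 169. The 80% rule is a participant-level trigger for the Day 360 visit, not a forecast.
- That the model creates a false gap between doses at Day 180. It can make the gap too large or too small, depending on when fading starts (Step 4).
- That the trial cannot detect fading. The MMRM at Day 180 and Day 270, the MMRM window contrasts and the PK/PD analyses are unaffected.

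The analysis is exploratory. The point is worth correcting but does not touch the primary result.

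**What to change.** Reconcile the statements in SAP Section 4.5.4 and name one main method per target.

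- **Two windows:** make the direct dose-response fit already described there the main method, after imputation under the efficacy estimand as the section states.
- **Day 180:** limit the PDT to this target, fitted on visits up to Day 180, with `t_Q` and the visits stated. Report the direct Day 180 fit as a sensitivity analysis. Which of the two leads is a precision-bias trade-off for the sponsor to decide and record.
- **Imputation for the direct Day 180 fit:** state it, since the section does not. SAP Section 4.1 has a usable rule for ANCOVA analyses: "missing data will be imputed using the multiple imputation method under the missing at random assumption". It could be applied to data before any intercurrent event, fitting the model to each imputed data set and pooling the posterior draws.
- **Fit criterion:** say what counts as poor fit of the PDT.

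The cost is SAP wording and a little more code. Credible intervals for the windows widen slightly (SE about 1 to 4% larger at assumed correlations of 0.8 to 0.4). A PDT extended with a dose-specific decline after the plateau is a possible alternative, but the SAP does not specify one.
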